6.0 Number of Subjects

48 participants will be enrolled in this research study.

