10.0 Study Design / Methods

Multidisciplinary Team. We have assembled diverse talents to develop translational approaches to TMS treatment development for opiate dependence. Our team has extensive experience in: 1) TMS ([name]), 2) NIH trials in chronic lower back pain ([name], [name]), 3) pain management ([name]), 4) neuroimaging ([name]), and 5) statistical modeling ([name], [name]). In addition to providing critical effect size data for a planned R01, this grant will provide an opportunity for several MUSC trainees in the DART Resident research program ([name]), and a NIDA T32 ([name] [name]) to get hands-on training with neuroimaging, TMS, and opiate dependent individuals. [name] will serve as a scientific advisor and meet regularly with the team to provide insight on outcomes and patient recruitment.

Overview. The proposed study will be the first to employ a randomized, double-blind, sham-controlled design to parametrically evaluate the longitudinal effects of 16 days of rTMS to the DLPFC (Aim 1) or the MPFC (Aim 2) on self-reported pain and the brain's response to pain. This will be done in a cohort of patients recruited from MUSC clinics and the outer community with chronic lower back pain. Participants will be randomized to receive TMS to the DLPFC, MPFC, or sham (50% at each site), using a Latin square randomization. Resting state connectivity will be collected at each MRI scanning session.. Quantitative Pain Testing will be collected 12 times. MRI data will be collected 3 times: before the 1st visit of TMS, before the 12th visit of TMS, and before the 16th visit of TMS.

Table 1. Study Design. Aim 1&2 will be conducted in parallel.

^primary goal: evaluate 2 TMS strategies as tools to decrease acute pain and brain reactivity to pain.

^secondary goal: durability

Screening	Group Assignment	Induction Phase				Maintenance Phase				Follow Up Phase							
		Week 1	2	3	4	5	6	7	8	9	10	11	12	13	14	15	16
	TMS Sessions	XXX	XXX	XXX	XXX	X	X	X	X								
	Clinical Assessments	XXX	XXX	XXX	XXX	X	X	X	X	X	X	X	X	X	X	X	
	Quantitative Urinalysis	X	X	X	X	X	X	X	X	X	X	X	X	X	X	X	
	Quantitative Pain Testing	X	X	X	X	X	X	X	X	X	X	X	X	X	X	X	
	Neuroimaging				X				X								

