Participants. We will enroll 48 men and women 18-75 years old with CLBP that have a history of current prescription opioid use (>3 months) for the treatment of pain. Participants will be recruited through the community along with MUSC clinics. Patients that have previously agreed to be contacted for research and have current chronic pain will be referred to the study. Our prior history with targeted enrollment (See Significance) indicates this is feasible within 20 months, leading to full completion by 22 months. **Exclusion criteria:** Typical MRI and TMS exclusionary criteria, including metal above the neck or implanted in the body, use of prescription medications that lower seizure threshold, a history of seizures or traumatic brain injury, pregnancy or trying to become pregnant, current substance use or dependence (other than opioids and nicotine), history of seizure disorder, and claustrophobia. Participants will provide written informed consent following explanation of the study. **Sample size estimate:** A power estimate for Aim 1 and 2 was prepared using an original fMRI dataset previously collected in our laboratory (8). In this experiment, 18 healthy controls performed the same fMRI pain paradigm as the present study before and after a single session of 10 Hz rTMS. Mean parameter estimates for the “heat pain vs. rest” condition were extracted from several *a priori* regions of interest. These data yielded an effect size which ranged from 0.70 (thalamus) to 1.08 (insula) (n=15 yields 80% power using a two-sided p<0.05). Allowing for a 10% dropout rate after the screening visit, and up to a 20% dropout rate at the end of the Treatment phase (Week 4), as well as a 10% data loss rate for MRI (Aim 2) due to individuals with excessive head motion in the MRI scanner, screening 58 individuals should lead to complete data from 48 individuals (16 real DLPFC, 16 real MPFC, 16 sham (50% at each site)). Randomization will be handled by the MUSC data coordination center of the Biostatistical Unit ([name], biostatistician) and a Latin Square design with replacement will be used to ensure even enrollment across groups with replacement.

General Methods

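### The 80% power claimed for n=15 is shown only at the top of the quoted effect range (1.08), not at 0.70; the test, the unit of n and the scaling of the effects are not stated

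*Combined protocol and SAP*

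**What the plan says.** The sample size paragraph of section 10.0 (Study Design / Methods) takes its effects from an earlier experiment of the same laboratory, in which "18 healthy controls performed the same fMRI pain paradigm as the present study before and after a single session of 10 Hz rTMS". Heat-pain-versus-rest parameter estimates were taken from prespecified regions, and the paragraph concludes: "These data yielded an effect size which ranged from 0.70 (thalamus) to 1.08 (insula) (n=15 yields 80% power using a two-sided p<0.05".

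It then allows for "a 10% dropout rate after the screening visit, and up to a 20% dropout rate at the end of the Treatment phase", "as well as a 10% data loss rate for MRI (Aim 2", and states that "screening 58 individuals should lead to complete data from 48 individuals", 16 in each of three groups (DLPFC, MPFC, sham). It adds that "a Latin Square design with replacement will be used to ensure even enrollment across groups with replacement". Section 6.0 says "48 participants will be enrolled in this research study".

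The neural comparison could be of either kind. The exploratory paragraphs in sections 1.0 and 10.0 call the MRI visit 1 to visit 2 comparison primary. The neuroimaging part of the Data Analysis Plan announces both within-subject and between-group models. The closing paragraph of the analysis section plans neural effect sizes for each active site relative to sham. On purpose, section 10.0 says of the grant: "In addition to providing critical effect size data for a planned R01".

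**The concern.** One power figure stands beside a range of effects, and four things needed to read it are absent: the test, the effect it refers to, whether 15 means pairs or patients per arm, and the SD used to standardise. A reader will probably take 80% to cover the whole range and, because the design is sham-controlled, to cover active against sham. Neither is shown.

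The source effects are before-after measurements in healthy controls after one session. No sham contrast and no MPFC stimulation are described for that experiment, so the effects do not directly support power for an active-versus-sham neural comparison.

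This sentence is the sole stated basis for 16 per arm. The trial is meant to supply effect sizes for a larger study, so the expected precision of those estimates matters at least as much as power. No precision is given.

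**Working it through.** **Inputs** (sample size paragraph, section 10.0): standardised effect d = 0.70 and 1.08; n = 15; two-sided alpha 0.05; target 16 complete per arm. No SD or pre-post correlation r is given.

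**Method.** Noncentral t. Two-sample, n per arm: noncentrality d·sqrt(n/2) on 2n−2 df. Paired, n pairs: noncentrality d·sqrt(n) on n−1 df.

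**1. The plan's own figure (n = 15, values taken as the test's own effects)**

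| Test | d = 0.70 | d = 1.08 | smallest d with 80% |
|---|---|---|---|
| Two-sample, 15 per arm | 0.70·sqrt(7.5) = 1.917; 45.7% | 1.08·sqrt(7.5) = 2.958; 81.5% | 1.06 |
| Paired, 15 pairs | 0.70·sqrt(15) = 2.711; 71.3% | 1.08·sqrt(15) = 4.183; 97.3% | 0.78 |

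The figure reproduces at one point. The two-sample test at 1.08 needs 14.5 per arm for 80%, which rounds up to 15. At 0.70 the requirement is 34 per arm (33.02) or 19 pairs (18.03).

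**2. Can raw-SD scaling rescue 0.70?** With equal pre and post SDs, d_change = d / sqrt(2(1−r)). Setting d_change to the 80% threshold d80 gives r = 1 − (0.70/d80)²/2.

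- Paired: 1 − (0.70/0.778)²/2 = 0.595, about 0.60.
- Two-sample: 1 − (0.70/1.060)²/2 = 0.782, about 0.78.

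At r = 0.5 the divisor is 1 and the table in step 1 is unchanged. Since r is not given, the range over assumed values at n = 15 and d = 0.70 is:

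| Assumed r | Paired | Two-sample on change |
|---|---|---|
| 0.3 | 56.9% | 34.7% |
| 0.5 | 71.3% | 45.7% |
| 0.7 | 90.2% | 66.6% |
| 0.8 | 97.8% | 83.3% |

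**3. At the planned 16 complete per arm (values as SD-of-change effects)**

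| Contrast | d = 0.70 | d = 1.08 | smallest d with 80% |
|---|---|---|---|
| Visit 1 to 2 change within one arm | 74% | 98% | 0.75 |
| One active arm vs sham | 48% | 84% | 1.02 |

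The second row treats a before-after effect as an active-minus-sham difference. That requires zero mean change under sham and equal SDs. As an illustration, a sham change of 0.2 SD in the same direction leaves a net 0.50 and about 28% power.

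95% CI half-width for active minus sham: t(0.975, 30)·sqrt(2/16) = 2.042 × 0.354 = 0.72 SD of change, slightly more than the 0.70 effect itself.

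**4. Completers (separate supporting point)**

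- Losses in turn: 58 × 0.9 × 0.8 × 0.9 = 37.6, or 12.5 per arm.
- If the 20% already includes the 10%: 58 × 0.8 × 0.9 = 41.8, or 13.9 per arm.
- Screened for 48 complete: 48/0.648 = 74.1, so 75; or 48/0.72 = 66.7, so 67.

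**The case against.** **The sentence is not wrong as it stands.** The parenthesis directly follows the insula value, and 15 per arm is exactly the two-sample requirement at 1.08. A reader might infer an arithmetic error. The documents do not support that: the figure reproduces at 1.08, they never say that 80% holds at 0.70, and raw-SD scaling with a high correlation could make it hold there. What stands is that the claim is not shown across the range.

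**The comparison tests are the reader's choice.** The plan specifies multivariate pattern analysis and names neither t-test for the imaging outcome. Pooling the two active arms against sham (32 vs 16) gives 61% at 0.70 and 93% at 1.08. This is fair, and it is why the contrast has to be named; no one figure here can be called the trial's power. Pooling also still misses 80% at 0.70 if the values are SD-of-change effects.

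**A different task.** One might infer that the source effects come from a task this trial does not run. That is unsettled. The sample size paragraph says the paradigm is shared, and the neuroimaging analysis models hot and warm thermal blocks, but the MRI scanning description lists only anatomical and resting-state scans.

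**Fewer than 16 per arm.** One might infer that the trial will end with 12 to 14 per arm. The 20% is an upper limit and replacement is planned, so this does not follow. Only the sum from 58 screened to 48 complete fails at the stated rates.

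**It is a pilot.** True, and no confirmatory decision hangs on the sentence. But the protocol makes the 80% claim itself, and a study meant to yield effect sizes should state their expected precision.

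**Conclusion.** The concern holds as a reporting gap with a real consequence. It is worth correcting, but it is not a proven error and does not show that the trial is underpowered. On the plain reading, the 80% belongs to the largest quoted effect under a two-sample test. At the smallest effect, power at n = 15 is 45.7% (two-sample) or 71.3% (paired). These figures rest on one assumption: that 0.70 and 1.08 are already on the scale of the test. If they are raw-SD effects, the result depends on an unstated correlation, and 80% at 0.70 needs r of at least about 0.60 or 0.78. Any active-versus-sham figure also assumes no mean change under sham and equal SDs. The point concerns the fMRI power statement only. The completer shortfall (about 38 to 42 against 48) is a separate inconsistency, which planned replacement may resolve.

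**What to change.** 1. Check in the source dataset whether 0.70 and 1.08 were divided by the SD of change or by the raw SD. If by the raw SD, obtain the observed pre-post correlation.

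2. Replace the parenthesis with wording such as:

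> Effects were standardised by [SD of change | raw SD, observed r = __]. Power is for [the visit 1 to visit 2 change within an arm, n pairs | the difference in that change between one active arm and sham, n per arm, assuming zero mean change under sham and equal SDs], two-sided 0.05, n = __ complete: __% at 0.70 and __% at 1.08. The effects are reference values from healthy controls after a single 10 Hz session. Effects relative to sham will be reported with 95% CIs, expected half-width __ SD of change.

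For SD-of-change effects and 16 complete per arm, the within-arm entries are 74% and 98% (80% at d = 0.75). For one active arm against sham they are 48% and 84% (80% at d = 1.02; half-width 0.72). For raw-SD effects, divide each by sqrt(2(1−r)) and recompute.

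3. Do not describe the source as a different task until the sample size paragraph, the MRI scanning description and the neuroimaging analysis agree on whether a heat-pain task is scanned.

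4. Separately, restate the completer count, or say explicitly that replacement restores 16 per arm. At the stated rates, 48 complete needs about 67 to 75 screened. Also reconcile the 48 enrolled in section 6.0 with the 48 complete in section 10.0.

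**Cost:** wording and one look at existing data. The power restatement needs no extra participants. The price is a less favourable stated power.

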1.0 Objectives / Specific Aims

Effective control of chronic pain is a top priority in the United States, as approximately 10% of adults have severe chronic pain – most of which is chronic lower back pain (CLBP). However, despite the advances in neuroscience over the past 20 years, we still largely treat chronic pain with opiate narcotics, much as was done in the Civil War. In addition to their high abuse liability and dependence potential (1), only 30–40% of chronic pain patients declare they receive satisfactory (>50%) relief from their pain through pharmacological treatment (Attal et al., 2006). In these patients a common clinical practice is to escalate the dose of opiates as tolerance develops – which unfortunately has contributed to escalation in opiate overdose deaths (2), a resurgence of intravenous heroin use, and \$55 billion in societal costs (3). **Consequently there is a critical need for new, treatments that can treat pain and reduce reliance on opiates in individuals with chronic pain.**

The goal of this R21 proposal is to evaluate 2 novel non-invasive brain stimulation strategies to mitigate pain and the brain's response to pain in CLBP patients that are currently taking chronic opiates, or that are seeking an alternative treatment for pain. Transcranial Magnetic Stimulation (TMS), can induce long term potentiation (LTP-like) and long term depression (LTD-like) effects on brain activity in a frequency dependent manner. Our group has previously demonstrated that LTP-like TMS to the dorsolateral prefrontal cortex (DLPFC, a node in the Executive Control Network (ECN)) can decrease perceived pain and corresponding BOLD signal in the ‘Pain Network’ (7, 8, 10-12). The Pain Network is an expansion of the Salience Network (SN; insula, dorsal anterior cingulate) which includes the thalamus and somatosensory cortex(4-6). The analgesic effects of DLPFC TMS can be blocked by naloxone – suggesting that the analgesic effects of LTP-like DLPFC TMS are opiate mediated. Additionally, DLPFC TMS delivered postoperatively leads to less patient administered morphine use (PCA-pump) in the hospital and less opiate use in the outpatient setting (9). **These data all suggest that LTP-like DLPFC TMS is a promising candidate for treating pain (Strategy 1, Aim 1).**

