SubAim 1: Evaluating Pain using Clinical Assessments Quantitative Sensory Testing (QST). Using the Medoc ATS thermal stimulator (Medoc Ltd Advanced Medical Systems, Ramat Yishai, Israel), 3 primary outputs will be compiled for each individual via the method of limits (54): sensory threshold, pain threshold, tolerance threshold. The thermode will be attached to the right forearm, and when the procedure begins it will begin heating from room temperature (32°C) at 0.2°C per second. Participants will indicate when they first detect the temperature change (sensory threshold), when it becomes painful (pain threshold), and when they can no longer tolerate the stimuli (tolerance threshold). When participants indicate tolerance, the operator will initiate rapid (>8°C per second) cooling. For safety, the thermode will be unable to exceed 51° and will initiate rapid cooling at that point. QST will be performed at two timepoints for each visit – prior to the initial MRI session and after the second MRI session. **Pain Questionnaire.** In order to evaluate current levels of pain, we will ask participants to rate their current level of pain and discomfort (scale, 0 through 10), each time the participant comes in (Table 1). On days where the individual receives rTMS, they will fill out this assessment before and after each session. **Pain and Craving Questionnaire:** In addition to the Pain Questionnaire above, participants will also rate their urge to use a pain reliever (Scale 0 – 10) and the amount they would be willing to pay for a pain reliever (In US Dollars). This questionnaire will be used at the same time during each intervention visit as the Pain Questionnaire (Table 2).

SubAim 2: Evaluating Pain using Neuroimaging Data At baseline we expect that people with chronic pain will have elevated activations in the Pain Network. This will be analyzed through the resting state connectivity network. Following sham stimulation, we do not anticipate a significant reduction of this response. Based on prior studies by our group in non-opiate dependent individuals, following LTP-like stimulation of the DLPFC, we expect a significant amplification of the DLPFC (% BOLD signal change), and a reduction of the Pain Network (dACC, anterior insula) reflecting the increased influence of executive processes. MPFC TMS however will likely not have as large of an effect on ECN engagement during the instruction to Control the pain.

Data Analysis Plan.

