performed using Statistical Parametric Mapping 12 (SPM12) in Matlab 2013 (Mathworks). Functional data will be corrected for magnetic field inhomogeneity and realigned (rigid-body, minimizing least squares differences) to the first image in the time series (Realign: Estimate and Unwarp). Non-linear deformations required for standard space normalization will be derived from each participant's anatomical image via a unified segmentation approach (Segment). After the mean realigned and unwarped functional image is coregistered to the skull stripped anatomical image (Coreg: Estimate) forward deformations (subject space to MNI standard space) will be applied (Normalise: Write). Finally, the data will be smoothed by an 8 mm full width half maximum Gaussian smoothing kernel (Smooth). Within-subject and between-group modeling. Data will be analyzed at the subject level using multivariate pattern analysis (Wager et al 2013 "An fMRI-Based Neurologic Signature of Physical Pain" new England Journal of Medicine). The six motion parameters (translations and rotations) will be included in the design matrices as covariates to account for non-task signal. The hot and warm blocks of thermal stimulus, as well as rating events, will be separately modeled in a boxcar fashion. Resting State Connectivity will be measured to compare MRI scan 1 to scan 2 – immediately after the treatment. MRI scan 3 will also be compared to these scans to see if there is a sustainable reduction in pain activity between these networks. Additionally factor analysis will be used to investigate the durability of the effects of each strategy on functional connectivity in each of the 3 Core networks (SN, ECN, DMN) using factor analysis longitudinally. **Covariates:** As an exploratory analysis we will also quantify the impact of several covariates which have previously been documented to affect the brain response to pain and pain thresholds (sex, Becks Depression Inventory score, length of time using chronic opiates). Although all participants will have taken their daily dose of opiates, which has a stable pharmacokinetic profile, we will also consider time since last dose.

Expected (and alternative) Outcomes:

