Exploratory Analysis: We will evaluate if there are rate-dependent effects between baseline SN connectivity with the ECN and DMN and the efficacy of each TMS strategy on subjective pain. Data will be analyzed by using multivariate pattern analysis (MVPA) (2014). While the primary outcomes will be MRI V1 vs V2, we will also examine the relative ‘durability’ of the effects on pain by comparing the MRI data at the 1 month follow up between and within groups with factor analysis. **Integration of Brain based and Behavioral Based Outcomes with Gender and other Demographic Variables:** Finally, we will compare the relative efficacy of these two types of TMS using the behavioral and neuroimaging measures. Specifically, we will determine the effect sizes for DLPFC and MPFC (relative to sham) stimulation on reducing the 1) the neural and 2) behavioral responses to pain, as well as 3) changes in clinical assessment metrics (see Approach). We will investigate the role of baseline cortical responsiveness on the pain response, as well as how changes in that evoked response are related to changes in both pain and craving measures. This will be specifically addressed as a factor of gender as well, given that there are established differences in sensitivity to pain and prevalence of opiate dependence between men and women.

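### The imaging outcome called primary has no lead measure and no multiplicity rule, and the stated 80% power does not hold across its own range of effect sizes

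*Combined protocol and SAP*

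**What the plan says.** Two places, the Exploratory Aim in Section 1.0 and the Exploratory Analysis in Section 10.0, give imaging primary status in the same words: "While the primary outcomes will be MRI V1 vs V2". Neither names a region, a network pair or a score.

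The target of the imaging hypotheses varies:

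- Section 1.0 defines four regions: "The Pain Network is an expansion of the Salience Network (SN; insula, dorsal anterior cingulate) which includes the thalamus and somatosensory cortex".
- SubAim 2 in Section 10.0 lists two, and adds a predicted rise outside the Pain Network: "we expect a significant amplification of the DLPFC (% BOLD signal change), and a reduction of the Pain Network (dACC, anterior insula").
- The sample-size paragraph of Section 10.0 says that estimates "were extracted from several *a priori* regions of interest", without a count or a leading region.

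That paragraph also holds the only alpha in the document: "These data yielded an effect size which ranged from 0.70 (thalamus) to 1.08 (insula) (n=15 yields 80% power using a two-sided p<0.05"). It claims this power for Aims 1 and 2.

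The neuroimaging part of the Data Analysis Plan (Section 10.0, item C) names multivariate pattern analysis, comparisons of resting-state connectivity between scans, and factor analysis. It gives no alpha, no correction, and no voxel or cluster threshold. The Exploratory Analysis compares each of the two strategies with sham. The Assessments paragraph of Section 10.0 instead takes the primary measures from QST.

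**The concern.** Followed as written, the plan lets a change in any one region count as support for an Aim, and the two strategies could be credited on different regions. A statement that a strategy dampens the Pain Network could then rest on whichever region happened to move. The pilot purpose suffers too: choosing the region that moved most inflates the effect size carried into the planned R01.

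The sample-size sentence adds to this. It gives one n and one power for a range of regional effects, so it is unclear which imaging hypothesis the 80% describes.

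**Working it through.** **1. The plan's power figure.** Inputs from the sample-size paragraph: d = 0.70 (thalamus) to 1.08 (insula), n = 15, two-sided alpha 0.05. The test is not stated. I take n as per group, since the planned arms are 16.

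- Two-sample t-test: noncentrality d√(n/2), 28 df. At d = 1.08, 1.08 × √7.5 = 2.96, power 82%. At d = 0.70, 0.70 × √7.5 = 1.92, power 46%.
- Paired t-test: noncentrality d√n, 14 df. At d = 1.08, 1.08 × √15 = 4.18, power 97%. At d = 0.70, 0.70 × √15 = 2.71, power 71%.
- Smallest effect with 80% power at n = 15: 1.06 (two-sample) or 0.78 (paired).
- For 80% at d = 0.70: 34 per group (two-sample) or 19 participants (paired).

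So the figure reproduces in a two-sample test only near the insula value. Neither two-sided reading gives 80% at the thalamus value. At alpha 0.025, the Bonferroni level for two contrasts, two-sample power with 15 per group is 72% at d = 1.08 and 34% at d = 0.70.

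**2. How many tests?** The documents do not say. Four Pain Network regions (Section 1.0) and two strategies make 4 × 2 = 8. Two regions (SubAim 2) and two strategies make 2 × 2 = 4. One Aim on its own has 4 or 2.

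**3. Chance of at least one null hit.** For k independent tests it is 1 − 0.95^k: 9.8% for k = 2, 18.5% for k = 4, 33.7% for k = 8. Independence is implausible, because the regions belong to one network and the strategies share a sham group. I therefore simulated null trials: 16 per arm, normal change scores, each active arm against the pooled sham by two-sample t-test at two-sided 0.05, and equal correlation ρ between regions. The values of ρ are assumptions. Separate runs agreed to about one percentage point.

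| Family | ρ = 0.8 | ρ = 0.5 | ρ = 0 | Reductions only, ρ = 0.8 to 0 |
|---|---|---|---|---|
| 4 regions, 2 strategies | 20% | 27% | 32% | 10% to 17% |
| 4 regions, 1 strategy | 12% | 16% | 18% | 6% to 10% |
| 2 regions, 2 strategies | 14% | 16% | 18% | 7% to 9% |
| 2 regions, 1 strategy | 8% | 9% | 10% | 4% to 5% |
| 1 measure, 2 strategies | 9% | 9% | 9% | 5% |

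The last row shows why one named measure still needs an adjustment for two contrasts.

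**The case against.** **The plan does not say that regions will be tested one by one at 0.05.** This stands. A reader might infer it from the sample-size sentence, but that sentence concerns an earlier dataset. The imaging plan names a multivariate method that could give one score per person. It does not, however, say that one such score is the primary outcome. It also models hot and warm thermal blocks, although the scan list in Section 10.0 contains only an anatomical and a resting-state acquisition. A single score is possible but not specified.

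**A false Pain Network effect in about a third of null trials.** A reader might reach this by counting five regions, two strategies and hits in either direction (32% at ρ = 0.5), or eight independent tests (33.7%). The first count includes DLPFC, which Section 1.0 places in the executive control network. The second ignores correlation. The hypotheses are also directional. One Aim read on SubAim 2's two regions, counting only reductions, gives no more than about 5%.

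**All three core networks belong to the primary comparison.** The documents do not support this. The text on "functional connectivity in each of the 3 Core networks (SN, ECN, DMN") concerns durability, which Table 1 makes a secondary goal.

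**The power may be paired.** The effect sizes come from a before-and-after experiment, so this is a fair reading. It lifts the insula figure to 97% but leaves the thalamus figure at 71%, and a paired test makes no comparison with sham.

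**This is a pilot for effect sizes.** That is largely right, and the Exploratory Analysis extends it to neural responses. It makes exploratory labelling acceptable. It does not excuse the absence of a named measure while hypotheses are stated and 80% power is claimed for both Aims.

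**QST may be the real primary.** Both statements that make imaging primary sit under exploratory headings. If the sponsor confirms QST, the imaging family becomes secondary and labelling is enough.

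**Conclusion.** The point holds as a gap in pre-specification. Imaging is called primary, its target shifts between two and four regions plus DLPFC, two strategies share one sham group, and there is no lead measure, correction or image threshold.

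If regions are tested separately at two-sided 0.05, the chance of at least one null hit is about 20% to 32% for four regions and two strategies, 12% to 18% for four regions and one strategy, and 14% to 18% for two regions and two strategies. Hits in the predicted direction are about half of these. The ranges rest on the assumed test counts, equal correlations of 0.8 to 0, normal change scores and 16 per arm. They are not predictions for the multivariate analysis that the plan names.

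The power statement needs correction whatever is decided on multiplicity: under either two-sided reading, 80% at n = 15 fails at the lower end of the quoted range.

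**What to change.** Before unblinding:

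1. Name one visit 1 to visit 2 imaging measure per participant, for example one Salience Network connectivity summary over dACC and anterior insula.
2. Test it as two contrasts, DLPFC against sham and MPFC against sham, with Holm or Dunnett at two-sided 0.05.
3. Label all other regions, networks and scan pairs exploratory, and report effect sizes with intervals.
4. Alternatively, if QST is confirmed as primary, label all imaging p-values exploratory.
5. In the sample-size paragraph, state the test and restate the power: with 15 per group in a two-sample test, 82% at the insula value (72% at alpha 0.025 for two contrasts) and 46% at the thalamus value, or 71% there if paired. Say also that these effects come from a heat-pain contrast, so they do not directly give the power of a connectivity measure.

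This changes wording only and needs no new data. The cost is a less favourable power statement and less freedom to choose a region afterwards.
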